5.4.4. Blood Pressure Stopping Criteria (Group 2 Only)

Subjects with a pre-dose systolic blood pressure of <90 mm Hg should not be dosed until systolic blood pressure is \geq 90 mm Hg.

[figure not shown]
5.4.5. Liver Chemistry Stopping Criteria

Liver chemistry stopping and increased monitoring criteria have been designed to assure subject safety and evaluate liver event etiology (in alignment with the FDA premarketing clinical liver safety guidance).

<http://www.fda.gov/downloads/Drugs/GuidanceComplianceRegulatoryInformation/Guidances/UCM174090.pdf>

Study treatment will be discontinued **for a subject** if liver chemistry stopping criteria are met:

Phase I Liver Chemistry Stopping Criteria – Liver Stopping Event Algorithm

Liver Safety Required Actions and Follow up Assessments Section can be found in [Appendix 2](#).

5.4.6. Plasma oxytocin concentration stopping criteria

Per Section 9.3.2.2, the plasma oxytocin concentrations in up to 5 subjects in Group 1 will be analysed in real time. If the plasma oxytocin concentration is BLQ or sufficiently low to prohibit interpretation in these 5 subjects irrespective of treatment, the study will be halted and reviewed.

5.5. Subject and Study Completion

A completed subject is one who has completed all phases of the study including the follow-up visit(s).

6. STUDY TREATMENT

6.1. Investigational Product and Other Study Treatment

The term ‘study treatment’ is used throughout the protocol to describe any combination of products received by the subject as per the protocol design. Study treatment may therefore refer to the individual study treatments or the combination of those study treatments.

Table 1 Study Treatment Information

	Study Treatment		
Product name:	Oxytocin (GR121619 capsule for inhalation)	Oxytocin	Oxytocin
Formulation description:	Powder Blend for Inhalation	Solution for Infusion	Solution for Infusion
Dosage form:	Inhalation powder, hard capsule	1ml ampoule	1ml ampoule
Unit dose strengths:	400 mcg 200 mcg	5 I.U./mL, or 10 I.U./mL	5 I.U./mL, or 10 I.U./mL
Route of Administration	For oral inhalation	Intramuscular (thigh)	Intravenous
Dosing instructions:	Capsule unit dose dispensed by ROTAHALER inhaler	Standard intramuscular injection	Adminster as a 30-second bolus
Physical description:	Colourless and clear HPMC capsules containing a white powder	Colourless and clear sterile solution	Colourless and clear sterile solution
Device:	ROTAHALER inhaler	Needle/Syringe	Intravenous Infusion Device

6.2. Medical Devices

The GSK manufactured medical device (or device manufactured for GSK by a third party) provided for use in this study is a high airflow resistance capsule-based inhaler (Modified Air Inlet ROTAHALER DPI device). **Although this investigational device bears a CE mark, it has not been CE marked in accordance with the Medical Devices Directive 93/42/EEC.**

Instructions for medical device use are provided in Section 6.7. Further details on use of the device are provided in the SRM.

GSK medical device incidents, including those resulting from malfunctions of the device, must be detected, documented, and reported by the investigator throughout the study – see Section 12.4.

6.3. Treatment Assignment

Subjects in Group 1 will be assigned to one of two treatments (IH oxytocin or IM oxytocin). Subjects in Group 2 will receive both IH and IV oxytocin in separate dosing sessions in a cross over design. Treatment assignment in Group 1, and order of dosing in Group 2, will be done in accordance with the randomization schedule generated by Clinical Statistics, prior to the start of the study, using validated internal software.

A description of each regimen is provided in Table 2:

Table 2 Treatment Assignment

Group	Session	Treatment ¹	Number of Subjects ²
Group 1	1	400 mcg IH oxytocin	10
		10 I.U. IM Oxytocin	10
Group 2, Cohort A	1	400 mcg IH oxytocin or 5 I.U. IV oxytocin	5
	2	400 mcg IH oxytocin or 5 I.U. IV oxytocin	
Group 2, Cohort B	1	400mcg IH oxytocin or 5 I.U. IV oxytocin	5
	2	400 mcg IH oxytocin or 5 I.U. IV oxytocin	

¹ See Section 6.4 for possible dose adjustment.

² See Section 9.2.2 for possible adjustment to subject numbers to Group 1

If deemed necessary or if there is a new site identified for conducting and/or continuing the clinical trial, then a new randomization schedule may be generated by Clinical Statistics, prior to the start of the study at the new site, using validated internal software.

6.4. Planned Dose Adjustments

There is no plan to adjust the dose of IH oxytocin in this study. However, if systemic exposure seen in 400 mcg IH oxytocin in TSL subjects is less than expected and not comparable to the 10 I.U. IM profile, a consideration to escalate the dose to 600 mcg may be made as detailed in Section 6.4.1.

For Group 2, if an exaggerated physiological response is seen with the IV dose, such as increased heart rate and decreased blood pressure, then consideration will be given to changing to a 5-minute infusion.

6.4.1. Dose Adjustment

The decision to adjust the IH dose in women in TSL will be determined by the GSK study team based on Group 1 PK data in TSL and Group 2, Cohort A PK data. After a minimum of n=5 women in TSL have received 400 mcg IH and 10 I.U. IM and a minimum of n=5 non-pregnant women on the combined oral contraceptive (Group 2, Cohort A) have received 400 mcg IH oxytocin, PK samples will be analysed and PK parameters derived (including but not limited to Cp10, Cp30 and AUC(0-3h)).

The median Cp10 will be estimated for women in TSL for each dose group (IH or IM) and the median ratio (IH/IM; n=5) derived. Based on the estimated ratio, the dose of IH oxytocin to be administered to women in TSL will either remain at 400 mcg or be increased per the criteria described in [Table 3](#):

Table 3 Dose Adjustment Decision Criteria

Median Ratio IH/IM	Decision
< 0.5	Consider study halt and review data.
≥ 0.5 to <0.7	Consider dose adjust to 600 mcg IH in women in TSL.
≥ 0.7	Continue with 400 mcg IH dose.

If a decision to increase the dose is made, additional subjects will be enrolled into Group 1 such that 10 subjects receive the 600 mcg IH oxytocin dose.

6.5. Blinding

This will be an open-label study.

6.6. Packaging and Labeling

The contents of the label will be in accordance with all applicable regulatory requirements.

6.7. Preparation/Handling/Storage/Accountability

- The investigator/designee will be trained to load the ROTACAPS powder capsule into the device, prime the dose and instruct the subjects to inhale from the ROTAHALER inhaler in the appropriate manner. The investigator/designee will always load and prime the ROTACAPS powder capsule in the device before the subject self-administers an IH oxytocin dose
- All subjects will be taught by the investigator/designee to use the device in the “full-tilt” position and to use a “fast and deep” inspiration technique per inhalation, to achieve two rapidly consecutive maximal inhalations for IH oxytocin administration. This will ensure optimal and consistent treatment delivery. For subjects, the training session will be at any time during the 28-day Screening Period, as deemed appropriate by the investigator/designee.
- ROTACAPS powder capsules should be kept in their sealed packaging at room temperature (15-25°C Centigrade [C]). The packaging should only be opened immediately prior to use.
- ROTAHALER inhaler devices will be supplied in bulk and unlabelled to the site. After dosing all ROTAHALER inhaler devices will be uniquely labelled and retained after each dosing session. The devices (which should not be opened up at

the clinical study site) will be stored until further instruction from the sponsor is received.

- The investigator or designee must confirm appropriate temperature conditions have been maintained during transit for all study treatment received and any discrepancies are reported and resolved before use of the study treatment.
- Only subjects enrolled in the study may receive study treatment and only authorized site staff may supply or administer study treatment. All study treatments must be stored in a secure environmentally controlled and monitored (manual or automated) area in accordance with the labelled storage conditions with access limited to the investigator and authorized site staff.
- The investigator, institution, or the head of the medical institution (where applicable) is responsible for study treatment accountability, reconciliation, and record maintenance (i.e. receipt, reconciliation and final disposition records).
- Further guidance and information for final disposition of unused study treatment are provided in the SRM.
- Under normal conditions of handling and administration, study treatment is not expected to pose significant safety risks to site staff. Take adequate precautions to avoid direct eye or skin contact and the generation of aerosols or mists. In the case of unintentional occupational exposure notify the monitor, Medical Monitor and/or GSK study contact.
- A Material Safety Data Sheet (MSDS)/equivalent document describing occupational hazards and recommended handling precautions either will be provided to the investigator, where this is required by local laws, or is available upon request from GSK.

6.8. Compliance with Study Treatment Administration

Per ROTACAPS powder capsule dose, each subject will be asked to inhale twice from the ROTAHALER inhaler to reduce the possibility of inadequate administration due to a single poor inhalation manoeuvre. If failure of the ROTACAPS powder capsule actuation is suspected by the investigator (i.e. due to failure to open the capsule during device priming), the investigator is permitted to rechallenge the individual with a maximum of two further administrations at the same dose using the same capsule.

When subjects are dosed at the site, they will receive study treatment directly from the investigator or designee, under medical supervision. The date and time of each dose administered in the clinic will be recorded in the source documents. The dose of study treatment and study subject identification will be confirmed at the time of dosing by a member of the study site staff other than the person administering the study treatment.

Group 1 – Women in TSL

Following randomisation and any pre-dose procedures, subjects will receive a single study treatment as active management of TSL. The specific timing of this dose will be as per local standard of care.²

Administration will be documented in the source documents and reported in the Case report form (CRF).

Group 2 – Non-pregnant, non-lactating females of child bearing potential

Following randomisation and all pre-dose procedures, subjects will receive two doses of oxytocin, separated by at least 48 hours. Randomisation will determine the order in which the IH and IV formulation is administered.

Administration will be documented in the source documents and reported in the Case report form (CRF).

6.9. Treatment of Study Treatment Overdose

For this study, any dose of the following compounds will be considered an overdose when administered as part of study procedures:

- IH oxytocin > 400 mcg
 - If study dose is increased to 600 mcg, then an overdose will be considered any dose > 600 mcg.
- Oxytocin > 10 I.U. IM
- Oxytocin > 5 I.U. IV

Note: Group 1 subjects may receive additional doses of oxytocin (IM or IV) when required as part of their general care and as clinically indicated. Additional doses of oxytocin will be recorded as concomitant medications, as will any related AEs.

General medical management consists of supportive care.

GSK does not recommend specific treatment for an overdose.

In the event of a study drug overdose the investigator or treating physician should:

1. Contact the Medical Monitor immediately.

² For information only: Standard of care at proposed clinical site is to administer the oxytocic drug by IM injection with the birth of the anterior shoulder, or immediately after the birth of the baby and before the cord is clamped and cut.

2. Closely monitor the subject for adverse events (AEs)/serious adverse events (SAEs) and laboratory abnormalities until oxytocin can no longer be detected systemically (at least 4 hours).
3. Obtain an additional plasma sample for pharmacokinetic (PK) analysis if requested by the Medical Monitor (determined on a case-by-case basis).
4. Document the quantity of the excess dose as well as the duration of the overdosing in the CRF.

Decisions regarding dose interruptions or modifications will be made by the investigator in consultation with the Medical Monitor based on the clinical evaluation of the subject.

6.10. Treatment after the End of the Study

Subjects will not receive any additional treatment from GSK after completion of the study because either only healthy volunteers are eligible for study participation, or there are other treatment options available.

The investigator is responsible for ensuring that consideration has been given to the post-study care of postpartum subjects' medical conditions, whether or not GSK is providing specific post-study treatment.

6.11. Lifestyle and/or Dietary Restrictions

6.11.1. Meals and Dietary Restrictions

There are no dietary restrictions for subjects in either cohort.

6.11.2. Caffeine and Alcohol

Group 1 – Women in TSL

- There are no restrictions for Group 1.

Group 2 – Non-pregnant, non-lactating females of child bearing potential

- During each dosing session, subjects will abstain from ingesting caffeine- or xanthine-containing products (e.g., coffee, tea, cola drinks and chocolate) for 12 hours prior to the start of dosing until collection of the final pharmacokinetic sample during each session.
- During each dosing session, subjects will abstain from alcohol for 12 hours prior to the start of dosing until collection of the final pharmacokinetic sample during each session.

6.11.3. Activity

Group 1 – Women in TSL

There are no activity restrictions.

Group 2 – Non-pregnant, non-lactating females of child bearing potential

Subjects will abstain from strenuous exercise for 48 hours prior to each blood collection for clinical laboratory tests. Subjects may participate in light recreational activities during studies (e.g., watch television, read).

6.12. Concomitant Medications and Non-Drug Therapies

6.12.1. Permitted Medications and Non-Drug Therapies

Paracetamol, at doses equal to or below the maximum recommended daily dose, is permitted for use during the screening period or at any time deemed necessary by the investigator or subject. All concomitant medication related to routine care during pregnancy and delivery is allowed (including pain relief [e.g. gas/air mixture] and epidural), and other medication may be considered on a case by case basis by the investigator or designee (in consultation with the Medical Monitor if required).

The start and stop time of any concomitant medications administered at any time during labour (including nitrous oxide gas/air mixtures) should be documented on the CRF.

6.12.2. Prohibited Medications and Non-Drug Therapies

Use of the following medications will result in immediate withdrawal of subject:

- Oxytocin for any reason (including, but not limited to, induction or augmentation of labour) before or after administration of study-related oxytocin.

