5.4.1. Pregnancy Complication Stopping Criteria (Group 1 Only)

Any complication requiring clinical intervention which no longer allows for a vaginal delivery or safe completion of study procedures will be cause for immediate withdrawal from the study. Investigators should continue to manage any pregnancy complication per local guidelines, and record any associated AE/SAE or concomitant medication. This includes the need for additional uterotonic administration.

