7.1.2. Time and Events – Main Phase Procedures**Group 1**

Procedure	Pre-dose	Time post dose										
		3 min	5 min	10 min	15 min	20 min	30 min	1 hr	2 hr	2.5 hr	3 hr	4 hr
Vital signs ¹							X		X			
Pharmacokinetic blood sample	X ²	X	X	X	X	X	X	X	X	X	X	X
Prior medication review	X											
Concomitant medication review		----- continuous review -----										
AE review		----- continuous review -----										
SAE Review		----- continuous review -----										
Device Acceptability Questionnaire ³												X
Full Blood Count	X											X

1. Includes blood pressure, heart rate, temperature, respiratory rate
2. Predose PK sample to be taken immediately prior to administration of study treatment
3. Only to be administered when randomized to IH oxytocin

Group 2 – Sessions 1 and 2

Procedure	Pre-dose	Time Post Dose														
		2 min	3 min	5 min	8 min	10 min	15 min	20 min	30 min	45 min	1 hr	1.5 hr	2 hr	2.5 hr	3 hr	4 hr
Brief Physical Exam	X															
Pregnancy Test	X															
Alcohol Breath Test, Smokerlyzer, Urine Drug Screen ¹	X															
Vital signs ²	X			X			X		X		X					X
12-lead ECG	X	X					X		X	X		X				X
Cardiac Telemetry		-----Continuous-----														
Spirometry ³	X											X				
Pharmacokinetic blood sample	X ⁵	X	X	X	X	X	X	X	X	X	X	X	X	X	X	X
Immunogenicity Sample	X															
Laboratory assessments (including liver chemistries)	X															X
Prior medication review	X															
Concomitant medication review		-----continuous review-----														
AE review		-----continuous review-----														
SAE Review		-----continuous review-----														
Discharge from unit ⁴																X

1. Smokerlyzer at Principal Investigator (PI)/designee discretion if smoking history in question.
2. Includes blood pressure, heart rate, temperature, respiratory rate, and SpO₂
3. FEV 1.0 will be performed in triplicate at each time point. Record all three values on source document, and record best effort in eCRF.
4. Discharge at PI discretion, no sooner than 4-hours post-dose.
5. 3 pre-dose samples: approximately 1 hr pre-dose, 30 minutes pre-dose, and 15 minutes pre-dose

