7.3.1.1. Time period and Frequency for collecting AE and SAE information

- Any SAEs assessed as related to study participation (e.g., protocol-mandated procedures, invasive tests, or change in existing therapy) or related to a GSK product will be recorded from the time a subject consents to participate in the study up to and including any follow-up contact.
- AEs will be collected from the start of Study Treatment until the follow-up contact (see Section 7.3.1.3), at the timepoints specified in the Time and Events Table (Section 7.1).
- Medical occurrences that begin prior to the start of study treatment but after obtaining informed consent may be recorded on the Medical History/Current Medical Conditions section of the CRF or appropriate source document.
- All SAEs will be recorded and reported to GSK within 24 hours, as indicated in [Appendix 3](#).
- Investigators are not obligated to actively seek AEs or SAEs in former study subjects. However, if the investigator learns of any SAE, including a death, at any

time after a subject has been discharged from the study, and she considers the event reasonably related to the study treatment or study participation, the investigator must promptly notify GSK.

NOTE: The method of recording, evaluating and assessing causality of AEs and SAEs plus procedures for completing and transmitting SAE reports to GSK are provided in [Appendix 3](#).

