7.3.4.2. Follow-up of Medical Device Incidents

- All medical device incidents involving an AE will be followed until resolution of the event, until the condition stabilizes, until the condition is otherwise explained, or until the subject is lost to follow-up (as defined in Section [5.4](#)). This applies to all subjects, including those withdrawn prematurely.

- The investigator is responsible for ensuring that follow-up includes any supplemental investigations as may be indicated to elucidate as completely as practical the nature and/or causality of the incident.
- New or updated information will be recorded on the originally completed form with all changes signed and dated by the investigator.

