7.5. Biomarkers

7.5.1. Pharmacodynamic Markers

Pre and post-delivery full blood counts will be collected from Group 1 subjects to assess for a change in haemoglobin levels.

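### In Group 1, withdrawing a woman because she was given oxytocin after her only study dose protects no one and ends scheduled observation where the uterotonic effect was insufficient

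*Protocol*

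**What the plan says.** Four places in the current protocol bear on a Group 1 woman who needs oxytocin after her study dose.

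- **Section 6.12.2** makes the following a cause of immediate withdrawal: "Oxytocin for any reason (including, but not limited to, induction or augmentation of labour) before or after administration of study-related oxytocin". It makes no exception for Group 1 or for rescue.
- **Section 6.9**, in a note on what counts as an overdose, says: "Group 1 subjects may receive additional doses of oxytocin (IM or IV) when required as part of their general care and as clinically indicated". Such doses are logged as concomitant medication. The note does not mention withdrawal.
- **Section 4.6.1** lists insufficient uterotonic effect as a risk of the inhaled product and gives additional uterotonics as the usual first step in managing it.
- **Section 5.4.1** orders withdrawal for complications that rule out vaginal delivery or safe completion of procedures. It then tells investigators to manage complications and record events and medication, and closes: "This includes the need for additional uterotonic administration". That sentence can attach to the withdrawal order or to the instruction to manage and record.

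On what is measured after the dose, section 7.5.1 says: "Pre and post-delivery full blood counts will be collected from Group 1 subjects to assess for a change in haemoglobin levels". The schedule in section 7.1.2 puts the post-dose count at 4 hours.

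**The concern.** A withdrawal rule for a prohibited medicine normally serves to stop further study treatment or to keep confounded subjects out of later dosing. Neither purpose applies here. Section 4.2 gives Group 1 one dosing session, so a woman rescued after it has no further study treatment to be kept from. Withdrawal then only ends the scheduled observations that remain.

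The loss is related to outcome. The women removed are those whose uterus did not respond well enough, which is what the exploratory haemoglobin endpoint is meant to reflect. If inhaled exposure in labour turns out low, a risk that section 4.6.1 itself raises, rescue could be more frequent in the inhaled arm. The remaining haemoglobin and questionnaire data would then look better than they should for that arm.

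The sections also give sites an unclear instruction. A site following 6.12.2 withdraws the woman. A site reading 6.9 and 4.6.1 could treat her, record the dose and carry on. Section 7 allows no waivers except for immediate safety concerns, so sites are not meant to resolve this locally.

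**Working it through.** The protocol states no figure for this point, so the check is a reading of the schedule followed by two scale calculations.

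**1. What a woman withdrawn before 4 hours loses (section 7.1.2, Group 1)**

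| Assessment | Planned | Lost |
|---|---|---|
| Full blood count | pre-dose, 4 h | 1 of 2, so no haemoglobin change |
| Device questionnaire ("Only to be administered when randomized to IH oxytocin") | 4 h | 1 of 1, inhaled arm only |
| Post-dose vital signs | 30 min, 2 h | both if withdrawn before 30 min; 1 if between 30 min and 2 h |

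Vital signs might still be available from routine care. Section 5.5 counts as completers only those who finish every phase including follow-up, so she is also a non-completer and, under section 4.3, may be replaced.

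**2. How many women (assumed rates)**

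The documents give no rescue rate, and inclusion criterion 7 selects women at low risk of postpartum haemorrhage. For an assumed rate p of post-dose clinical oxytocin among the 20 planned women, the expected number is 20p and the chance of at least one is 1 − (1 − p)^20.

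| p | Expected number | Chance of at least one |
|---|---|---|
| 1% | 0.2 | 18% |
| 5% | 1 | 64% |
| 10% | 2 | 88% |

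**3. Whether keeping these women in costs precision on the main comparison**

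The input is the AUC(0-3h) SD of 0.424 on the log scale (section 9.2, Table 5). The expected 90% half-width is exp[t(0.95, df) × c4(df) × 0.424 × √(1/n1 + 1/10)] − 1, with df = n1 + 8 and c4 the factor for the expected value of an estimated SD.

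- Plan's own case, n1 = 10: exp(1.734 × 0.986 × 0.424 × 0.447) − 1 = 38.3%, which matches Table 5.
- If 1, 2 or 3 values are missing in one arm and not made up (n1 = 9, 8, 7), the result is about 40%, 41% and 43%.

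These values are mostly unusable whether or not the woman is withdrawn, because rescue oxytocin is the measured analyte. The widening is therefore not a cost of changing the rule. If the numbers are made up to the roughly 20 evaluable women in section 9.2, the half-width stays at 38.3%.

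**The case against.** The strongest reply is that the sections answer different questions. The sentence in 6.9 sits in the overdose section, and its job is to say that clinical oxytocin is allowed and is not a study overdose. It is silent on study status. Of the two sections, only 6.12.2 sets status, and it sets it clearly. Both readings of the last sentence of 5.4.1 fit a sequence of treat, record, withdraw. This stands: a reader might infer that the protocol contradicts itself outright or leaves a rescued woman's status undefined, and the text does not support either. It does not rescue the rule, which on that reading still withdraws women for no protective purpose.

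A reader might also infer that withdrawn women lose safety follow-up. Section 7.3.1.1 says "Investigators are not obligated to actively seek AEs or SAEs in former study subjects", and only the device-incident section (7.3.4.2) adds "This applies to all subjects, including those withdrawn prematurely". That inference goes too far:

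- Section 7.3.1.1 collects adverse events from dosing until the follow-up contact. Nothing equates a woman withdrawn hours after dosing with a former subject.
- Section 12.3.1 makes lack of efficacy itself an adverse event.
- Sections 7.3.1.3 and 7.3.2 follow reported events and make haemorrhage and placental problems events of special interest.
- Section 4.6.1 plans an enquiry about late bleeding.

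What remains is that no section expressly says a woman withdrawn for rescue keeps both scheduled contacts.

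It is also fair that haemoglobin and the questionnaire are exploratory, that a 4-hour count would be taken after rescue treatment, and that section 7.3.10 ties the questionnaire to use of the inhaler, so it could be completed early. These points limit the harm without removing it.

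**Conclusion.** The concern holds as a badly fixed withdrawal rule, in tension with 6.9 and 4.6.1 and left unclear by 5.4.1. Its severity is minor to moderate.

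The loss per affected woman is one haemoglobin change, one questionnaire in the inhaled arm, up to two vital-sign sets, and completer status. It is selective, since it falls where the uterotonic effect was insufficient. That it would fall more often in the inhaled arm is a possibility and not something the documents show. The number affected depends entirely on the assumed rescue rate.

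A reader might go further and see a threat to the primary objective. The documents do not support that. Post-rescue concentrations are largely unusable under either rule. Section 9.3.1 keeps every dosed woman in the safety population and, if a sample was analysed, in the pharmacokinetic population. Section 9.2 enrols towards about 20 evaluable women.

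**What to change.** - In section 6.12.2, limit the withdrawal rule for Group 1 to oxytocin given before the study dose. Exclusion criterion 12 already bars pre-dose oxytocin, so no protection is lost.
- In section 5.4.1, reword the last sentence so that post-dose uterotonic rescue is managed and recorded and is not in itself a withdrawal criterion.
- State that rescued women complete the post-delivery blood count, the remaining vital signs and both follow-up contacts.

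The handling of concentrations drawn after rescue oxytocin can be left to the Reporting and Analysis Plan. No new replacement rule is needed, given section 9.2. The cost is amendment wording only.
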